12.1.10 Fresh biopsies

Optional lesional and non-lesional biopsy samples will be collected at selected US sites for exploratory analysis at baseline/predose on Day 1 and on Day 99/Week 14 during the double-blind period. These fresh biopsies will be shipped overnight to Allakos for additional cell phenotyping and other exploratory analysis. Once Allakos receives the biopsies, they will be dissociated into single cells and immunophenotyped for immune cell populations (lymphocytes, eosinophils, basophils, mast cells, neutrophils, and macrophages) and other exploratory analysis. Detailed instructions on collection, packaging and shipping will be included in the lab manual. All materials required for shipment of the additional samples will be provided to the site by the Central Laboratory. Subjects who choose to participate will need to sign a separate Information and Consent Form.

12.2 Safety-Related Procedures

12.2.1 Concomitant Medications

All concomitant medication and concurrent therapies will be documented at screening and at study visits if changes are made. Dose, route, unit, frequency of administration, indication for administration, and dates of medication will be captured. Any prior medication received within 30 days before screening and during the study through Day 169 (56 or 84 [± 5] days after last dose of study drug if ET) will be recorded, or through the first dose of study drug if subject enters the OLE period of the study.

For subjects participating in the OLE period, concomitant medications should be recorded in the AK002-018 double-blind treatment period database up until the first OLE dose is administered after the Day 99 visit. Rescue medications and procedures must be documented as rescue treatment in the source documents and on the Prior and Concomitant Medications eCRF.

Any medications taken for AD or AD-related symptoms at any time (even if longer than 30 days before screening) should be listed as concomitant medications, even if the medication was discontinued prior to study participation.

12.2.2 Complete Physical Examination

A complete physical exam will be performed by either the Investigator or a qualified designee during the screening visit. A complete physical exam will include the following body system or

organ assessments: skin; head, eyes, ears, nose, and throat; thyroid; lungs; cardiovascular; abdomen; extremities; lymph nodes; and a brief neurological examination.

12.2.3 Body Weight and Height

At screening, height (in cm) and weight (in kg) will be measured by the site and recorded. The site cannot use values stated by the subject. Body weight will also be measured on all dosing and follow-up days or 14, 56, and 84 days after last dose if ET.

12.2.4 Symptom-Directed Physical Examination

A symptom-directed physical exam of reported or observed subject symptoms warranting examination in the opinion of the Investigator, including assessments of possible injection site reactions and IRR, will be performed by either the Investigator or a qualified designee at all study visits during the treatment period and follow-up period. New, abnormal physical exam findings must be documented and will be followed by the Investigator or Subinvestigator at the next scheduled visit or sooner if clinically indicated or referred to a non-study physician.

12.2.5 Electrocardiogram

An ECG will be obtained during screening after the subject has been in the resting position for ≥ 5 minutes and before any blood draw. The Investigator or Subinvestigators will review and assess any abnormalities on the ECG in terms of clinical significance. The ECG (without intensive QT analysis) will be used to identify diseases or conditions that would put the subject at increased risk if participating in a clinical study, so this should be taken into consideration when evaluating eligibility for entry into the study.

12.2.6 Previous AD Diagnosis and Treatments Review

During the screening visit the Investigator or designee will collect documentation supporting the chronic AD diagnosis and ask the subject about the various treatments or methods of symptom control that they have tried in relation to their AD symptoms. The treatments may include medications (prescription or over-the-counter), therapies (i.e., phototherapy) or adaptive behaviors, as well as alternative medicine (i.e., acupuncture or hypnotic therapy). Any previous therapies and medications as related to subjects' AD disease will be recorded in the study CRF.

Required specific source documentation supporting the assessment of inclusion and exclusion criteria regarding history of AD diagnosis and treatments will be the following:

- A chronic AD diagnosis for at least 3 years (Inclusion Criteria #3) should be confirmed by historical medical records from a dermatologist, allergist, or immunologist, or via current documentation from a study dermatologist, allergist, or immunologist.

- Medical records documenting the topical AD treatments and reason for discontinuation are required for Inclusion Criteria #4. Notes from patient interview alone for previous treatment are not sufficient.
- Dermatologist or study doctor's notes regarding AD treatment history are needed for assessing Inclusion criteria # 9 and Exclusion Criteria #2.

More details are provided in the instruction of the Eligibility CRF page.

12.2.7 Vital Signs

Vital signs including systolic and diastolic blood pressure, pulse, body temperature, and respiratory rate will be taken after the subject has been at rest for ≥ 5 minutes and before any blood draw (except for post-SC injection when vital signs will be obtained as described below).

Vital signs will be measured at screening, on Day 8 (± 3), on all follow-up days or 14, 56, and 84 (± 5) days after last dose if ET, and on all dosing days within 30 minutes predose, 15 (± 5) minutes after completion of the SC injection, and just prior to discharge.

Additional vital signs measurements may be collected at the Investigator's discretion if an IRR occurs. Vital signs including systolic and diastolic blood pressure, pulse, body temperature, and respiratory rate will be measured after the subject has been at rest for ≥ 5 minutes and before any blood draws have been obtained (unless collected for an IRR).

Please refer to the schedule of assessments in [Table 1](#).

12.3 Clinical Laboratory Measurements

Blood and urine samples for clinical safety laboratory tests will be collected at the time points described below. Investigators may have additional laboratory tests performed for the purpose of planning treatment administration or following AE or abnormal laboratory values.

The site will process and ship blood and urine samples per central laboratory instructions. A central laboratory or designee will analyze blood and urine samples and provide results for the clinical safety laboratory tests.

Clinical laboratory testing may be performed locally, if necessary, with prior approval from Allakos. The site will strive to use the central laboratory whenever possible.

For any laboratory test value outside the reference range, the Investigator will determine clinical significance: Not Clinically Significant (NCS) or Clinically Significant (CS). An abnormal laboratory value should be deemed CS if any of the following conditions are met:

- The abnormality suggests a disease and/or organ toxicity that is new or has worsened from baseline.
- The abnormality is of a degree that requires additional active management, e.g., change of study drug dose, discontinuation of the study drug, close observation, more frequent follow-up assessments, or further diagnostic investigation.

Therefore, a clinically significant laboratory value is a lab test value that indicates a new disease process, an exacerbation or worsening of an existing condition, or requires further action to be taken.

For any laboratory test value outside the reference range that the Investigator considers clinically significant, the Investigator will:

- Repeat the test to verify the out-of-range value.
- Follow the out-of-range value to a satisfactory clinical resolution.
- Record as an AE any laboratory test value after start of study drug that:
 - The Investigator considers clinically significant.
 - Requires a subject to be discontinued from the study.
 - Requires a subject to receive treatment.

Blood will be obtained for CBC with differential as described in Section 12.1.9.

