12.1.9 Complete Blood Count with Differential

Blood for complete blood count (CBC) with differential, including absolute blood eosinophil count, will be obtained at screening, just prior to each SC injection, 1 hour (± 15 minutes) after the end of each SC injection, and on Days 99, 141, and 169 (± 5) or 14, 56, and 84 (± 5) days after last dose if ET. The blood sample will be processed and shipped in accordance with the Laboratory Manual and lab kit instructions. A central laboratory will analyze the blood sample and provide results for CBC with differential including hemoglobin, hematocrit, platelet count, red blood cell count, white blood cell count, and absolute differential count (neutrophils, lymphocytes, monocytes, eosinophils, and basophils).

During the double-blind period, all differential blood counts from Day 1 (post-dose) through the end of the subject's participation will be blinded to the Sponsor and the site. An unscheduled CBC may be collected at the request of the Safety Monitor. The blood differential test results (neutrophils, eosinophils, basophils, monocytes, and lymphocytes) will be blinded from the Investigator and Sponsor from post-dose Day 1 through Day 169 or ET and until database lock has occurred. If a subject continues to the OLE period of the study, all differential blood counts will be blinded for the first (OLE Day 1) predose assessments and will be unblinded after the subject has received the first dose of the study drug.

As described in the Investigator's Brochure, changes in certain lab results are a part of the expected effects of lirentelimab and could potentially introduce bias in blinded members of the study. The Safety Monitor will have real-time access to these laboratory results and will review and escalate any concerns/issues to the Medical Monitor and/or the site as appropriate. An

unscheduled CBC with differential may be collected if requested by the Safety Monitor. All panic alerts for blinded values will be sent to the Safety Monitor and evaluated in real time.

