20.11 Appendix 11: Open Label Extension Period (Optional)

20.11.1 Summary of the Open-Label Extended Dosing Period

Subjects who complete the double-blind, placebo-controlled treatment period (including the Day 99 study visit) and meet the open-label extended dosing eligibility criteria will be given the option to receive 7 doses of 300 mg lirentelimab SC through the open-label extended (OLE) dosing period.

On Day 99 (± 5 days) of the double-blind period, eligible subjects participating in the OLE period will begin following the OLE Schedule of Events ([Table 8](#)) and will no longer follow the double-blind period Schedule of Events ([Table 1](#)). If OLE Day 1 is completed on the same day as Day 99, already completed assessments (for Day 99) do not need to be repeated (for OLE Day 1), as long as they are performed within time frames noted in the [Table 8](#) notes.

The OLE dosing period is summarized as follows:

- The Investigator will evaluate whether the subject is eligible for OLE. If eligible, the subject will be given the option to participate in the OLE period and receive 7 doses of open-label 300 mg lirentelimab SC administered every 2 weeks starting on Day 99 of the double-blind period, which will be considered Day 1 of the OLE period. OLE dosing may be delayed for up to 7 days after completion of the Day 99 visit.
- On Day 99, after completing all Day 99 assessments, eligible subjects who choose to participate in the OLE period will begin following the OLE Schedule of Events ([Table 8](#)).
- Day 1 of the OLE can occur up to 7 days following Day 99 of the double-blind period. In case Day 1 of the OLE is not the same as Day 99 of the double-blind period, applicable subjects (women of childbearing potential) will have a urine dipstick pregnancy test.
- After OLE Day 1, subsequent doses will be given on OLE Days 15, 29, 43, 57, 71, and 85 (± 5 days).
- All differential blood counts will be blinded to the Sponsor and the site until after OLE Day 1 dosing.
- Subjects will remain at the site for at least 1 hour of observation after each dose. In the event of an IRR, the subject may require prolonged observation (>1 hour or until the symptoms resolve), as per Investigator discretion.
- Subjects will be followed for approximately 12 weeks after the last dose. Follow-up visits will occur on OLE Days 99, 141, and 169 (14, 56, and 84 [± 5] days) following the last dose of open-label study drug.

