6.12.2 Laboratory Test

Laboratory data will be summarized by presenting summary statistics of raw data and change from baseline values (means, medians, standard deviations, ranges). For quantitative laboratory parameters, both actual values and change from baseline values will be summarized at each visit.

Shift tables will be presented, in which, lab test results at baseline and post-baseline visit will be classified into below (<LLN), within (\geq LLN and \leq ULN), and above (>ULN) normal ranges. Subject incidences (n and %) will be presented for the shift from baseline to the post-baseline visits.

Note that the analysis window will be applied for the visits.

A complete laboratory data listing, including hematology, biochemistry, and urinalysis will be provided for all subjects.

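### The laboratory AE rule relies on an Investigator who cannot see post-dose differential counts, so non-escalated neutropenia and lymphopenia may be under-recorded, and no graded by-arm table makes up for it

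*Protocol*

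**What the plan says.** **The laboratory AE rule (Protocol 12.3).** The rule covers all tests: "For any laboratory test value outside the reference range, the Investigator will determine clinical significance: Not Clinically Significant (NCS) or Clinically Significant (CS". For values judged significant, the Investigator repeats the test, follows it to resolution and records an AE. Three conditions lead to an AE: a value that "the Investigator considers clinically significant", one that "Requires a subject to be discontinued from the study", or one that "Requires a subject to receive treatment". The section refers to 12.1.9 for blood-count collection and makes no exception for masked results.

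**The masking rule (Protocol 12.1.9; also 11.3 and Table 1 note 14).** The five white-cell differential results, among them the neutrophil and lymphocyte counts, "will be blinded from the Investigator and Sponsor from post-dose Day 1 through Day 169 or ET and until database lock has occurred". Section 11.3 puts the end point at final lock. The Safety Monitor has real-time access, receives all panic alerts for masked values, may ask for an unscheduled count, and escalates to the Medical Monitor and/or the site as it judges appropriate.

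**The open-label extension (Protocol 20.11.1).** "All differential blood counts will be blinded to the Sponsor and the site until after OLE Day 1 dosing". I read this as opening the extension-period counts after the first open-label dose; 11.3 keeps the double-blind counts masked until final lock.

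**The analysis.** AE summaries use events reported in the clinical database (Protocol 16.7), and all AEs must be coded before lock (Protocol 17.4, SAP 5.6). For laboratory data, SAP 6.12.2 plans summary statistics with ranges for values and changes at each visit, a complete listing, and shift tables with three classes, of which the lowest is a single one: "lab test results at baseline and post-baseline visit will be classified into below (<LLN".

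**The concern.** The two protocol rules cannot both be followed for the five differential counts after the first dose. The Investigator is told to judge values that the Investigator may not see. The Safety Monitor sees them, but is not given the task of deciding clinical significance, assigning a grade or entering an AE. Masking lasts until lock and AE coding must be finished by lock, so no later step is described at which the gap would be filled.

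At stake is the double-blind comparison of neutropenia and lymphopenia as AEs, for an antibody that depletes blood cells by design. The protocol treats these counts as relevant elsewhere: Appendix 11 extends follow-up when lymphocyte or eosinophil counts have not recovered, and opportunistic infections are AEs of special interest (14.3). If only part of the significant low counts reach the site, the AE tables understate the incidence in both arms and shrink any real difference between them.

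**Working it through.** The plan states no rate for these events and no escalation threshold, so it gives no figure to reproduce. The check is a count of masked samples, followed by tracing how a low count could reach a table.

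**1. Samples masked.** Inputs from Protocol Table 1 note 14 and 12.1.9: one sample at screening, one before and one about an hour after each of 7 injections, and one at each follow-up visit (Days 99, 141, 169). Only screening and Day 1 predose precede the masking.

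- Subject not entering the extension: 1 + 7 × 2 + 3 = 18 scheduled; 18 − 2 = 16 masked; 16/18 = 89%.
- Subject entering the extension, through Day 99: 1 + 7 × 2 + 1 = 16 scheduled; 16 − 2 = 14 masked; 14/16 = 88%.

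In both cases every post-dose value is masked. These are counts of measurements, not of abnormal results or lost AEs.

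**2. Routes from a low count to the AE tables.**

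| Route | Open for a masked count? |
|---|---|
| Investigator judges the central result | No |
| Safety Monitor escalates, site records AE | Possible; no threshold or duty to enter the AE stated |
| Value leads to discontinuation or treatment | Possible, once someone acts on the value |
| Investigator orders an additional test (12.3) | Possible; needs a reason to order it |
| Review of differentials after unmasking | Not described |

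An asymptomatic low count that is not escalated has no defined route.

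**3. Size, as illustration only.** Let p be the true incidence of a clinically significant low count in an arm of 65 (Protocol 11.2), and f the fraction escalated and recorded. Neither is in the documents; I assume p from 2% to 10% and let f run from 0 to 1. Expected subjects = 65p; recorded = 65pf; missing = 65p(1 − f).

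| f | Recorded, p = 2% | Recorded, p = 10% | Missing, p = 2% | Missing, p = 10% |
|---|---|---|---|---|
| 0 | 0 | 0 | 1.3 | 6.5 |
| 0.5 | 0.65 | 3.25 | 0.65 | 3.25 |
| 1 | 1.3 | 6.5 | 0 | 0 |

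If f is equal in the two arms, the recorded difference is f times the true difference: the AE table then attenuates a real effect but does not create one. Since f is unknown, the loss runs from none to all.

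**4. What the laboratory tables recover.** The by-visit minimum (SAP 5.1 and 6.12.2) shows the lowest count in each arm, but not how many subjects came near it. The listing shows every value but is not a tabulated comparison. The shift table counts subjects but has a single low category. Protocol Appendix 8 divides low lymphocytes into below LLN to 800/mm³, below 800 to 500, below 500 to 200, and below 200 (Grades 1 to 4); all four fall in the same shift cell. No output in SAP Appendix 2 gives subject incidence by worst grade and arm.

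**The case against.** The strongest case against is that this is a drafting gap in a system that works. The Safety Monitor watches the values in real time and gets every panic alert, so the most severe counts are the likeliest to be escalated. Once a value reaches the site, 12.3 applies as written. Because 12.3 refers to 12.1.9 for the blood count, a sensible reader might infer the exemption. Total white cell count, haemoglobin and platelets are not in the masked list. Infections are recorded as AEs in the usual way, an independent Data Monitoring Committee meets under a charter not included here, and masking is the same in both arms. Much of this stands, and it limits the claim.

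Three stronger readings are tempting and are not supported:

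- *That these AEs will be largely absent, for instance about 0% against 0%.* That requires f near 0. The documents do not fix f and do provide an escalation route.
- *That the SAP shows low counts only through the shift table.* It also plans by-visit summaries with ranges (Table 14.3.2.1) and a full hematology listing (Listing 16.2.3.2.1). Severe values are discoverable; what is missing is their incidence by grade and arm.
- *That the extension will show an artificial rise in cytopenia AEs.* Ascertainment does change when counts are opened, but extension AEs go to a separate database and the SAP plans no comparison between periods.

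What the objection does not answer is who decides significance, who grades, and who enters the AE for a masked count. Panic alerts do not settle it: 12.3 counts a value as significant if it only calls for close observation or more frequent follow-up, which may fall well below an alert level.

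**Conclusion.** The point holds in a limited form. Protocol 12.3 and 12.1.9 are unreconciled for every post-dose differential count, and no one is named to take over the Investigator's task. Followed exactly, the plan puts non-escalated neutropenia and lymphopenia at risk of under-recording in the double-blind AE tables, in both arms. The masked share is 16 of 18 scheduled counts for subjects not entering the extension and 14 of 16 for entrants. The number of lost AEs cannot be derived; the illustration above rests on assumed rates and an unknown escalated fraction.

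The laboratory outputs limit the damage but do not remove it, since none gives subject incidence by severity grade and arm. This is worth correcting because the correction is cheap and the data are already collected. It does not bear on the efficacy analysis.

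**What to change.** 1. **SAP 6.12.2 and Appendix 2.** Add one table for the Safety population: worst post-baseline CTCAE grade by arm for neutrophils and lymphocytes, from the central-laboratory values already collected. Footnote the AE tables to say that they may under-count these events because of masking. This part does not depend on the masked AE route, and the grade rests on numerical limits rather than judgement.

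2. **Protocol 12.3 and 12.1.9.** State that masked differentials are exempt from Investigator review for AE recording, and name who records their significance and grade. The Safety Monitor, who already reviews them, is the natural choice. Keep the entries in a restricted log, flagged as laboratory-derived, that is completed, coded and locked before the treatment code is released at each lock. Adding AEs after unblinding would break the lock conditions in Protocol 17.4 and SAP 5.6. Protocol 17.4 releases the code after a provisional Day 99 lock, so later entries should be made by someone still without it and closed before final lock. The repeat-test and follow-up duties in 12.3 need the same reconciliation with the masking; how to do that is a clinical matter for the sponsor.

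**Cost.** One extra table, a short protocol clarification and a restricted log kept by an existing role. One limit remains: whoever sees eosinophil counts may be able to infer the arm, so the significance call in the log is less well protected than the grade. That is a further reason to rely mainly on the graded table.

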12.3.1 Blood Chemistry Profile

Blood for chemistry, including hCG and FSH (only for screening), will be collected. Only subjects of childbearing potential and postmenopausal women are required to have hCG or FSH testing (as described in Section 12.3.2). Postmenopausal status must be confirmed by testing of FSH prior to the first dose of study drug regardless of the subject's age.

Blood for chemistry will be obtained predose on all dosing days, as well as during screening, and on Days 99, 141, and 169 or 14, 28, 56, and 84 (± 5) days after last dose if ET.

The blood sample will be processed and shipped in accordance with the Laboratory Manual and laboratory kit instructions. A central laboratory will analyze the serum sample and provide

results for chemistry tests including sodium, potassium, chloride, bicarbonate, glucose, blood urea nitrogen, creatinine, creatine kinase, calcium, phosphorus, magnesium, total and direct bilirubin, total protein, albumin, aspartate aminotransferase (AST), alanine aminotransferase (ALT), alkaline phosphatase, gamma-glutamyl transferase (GGT), and lactate dehydrogenase.

